### 10.1.2 Comparison: Laminectomy alone

Whilst individual techniques may vary slightly, the principles of a cervical laminectomy are as follows:

- The patient is positioned prone and the correct spinal level is identified
- A midline incision is made and dissection is undertaken down to the spinous process.
- A subperiosteal dissection to expose the spinous process, lamina and lateral masses of the desired levels is then performed.
- Fluoroscopy may be obtained to ensure the correct levels are removed.
- A posterior cervical laminectomy is then performed using one of the following techniques:
  - A high-speed cutting burr
  - A manual laminectomy using a combination of rongeurs
  - A footplate craniotome
- A subfascial drain can then be placed and the muscle, fascia and skin closed.

A list of the known complications of both of the above procedures are detailed in section 12.3.

## 10.2 Surgeon Experience and Eligibility

Both techniques, laminectomy and laminectomy plus fusion, belong to the standard repertoire of any spine surgeon. However, laminectomy alone can also be conducted by general neurosurgeons. This is well recognised within the spinal centres in the UK. The NHS standard contract for complex spine surgery outlines the necessity for collaboration between generalist surgeons and complex spine surgeon with orthopaedic or neurosurgical background for the treatment of degenerative neck conditions.

Whilst research, including a large retrospective multicentre study of 675 patients has not demonstrated that surgeon experience changes outcomes in patients undergoing posterior surgery for DCM, to mitigate risks of variations in outcome due to surgeon experience, we propose to:

- Only accept study sites capable of delivering both operations,
- Site PIs should be competent in both operations AND
- Will be responsible for ensuring surgeons performing an operation are sufficiently experienced to do so. We propose this includes ensuring they have performed and/or supervised the procedure at least 5 times in the preceding 12 months

## 11 Procedures and assessments

### 11.1 Participant identification

Local investigatory teams will identify and approach potential participants at each participating centre. It is likely that most potential participants identification will occur in the outpatient setting.

### 11.2 Consent

The Informed Consent form must be approved by the REC and must be in compliance with GCP, local regulatory requirements and legal requirements. The investigator or designee must ensure that each trial participant, or his/her legally acceptable representative, is fully informed about the nature and objectives of the trial and possible risks associated with their participation.

The investigator or designee will obtain written informed consent from each participant or the participant's legally acceptable representative before any trial-specific activity is performed. The informed consent form used for this trial and any change made during the course of this trial, must be prospectively approved by the REC. The investigator will retain the original of each participant signed informed consent form.

Should a participant require a verbal translation of the trial documentation by a locally approved interpreter/translator, it is the responsibility of the individual investigator to use locally approved translators.

Any new information which becomes available, which might affect the participant's willingness to continue participating in the trial will be communicated to the participant as soon as possible.

### 11.3 Screening evaluation

Potential subjects will be approached at neurosurgery centres at each participating centre. Most trial assessments will take place in outpatient clinic during routine hospital attendance. MRI scans will take place at the local radiology department.

#### 11.3.1 Screening Assessments

Potentially eligible patients with DCM will be approached by a delegated member of the local trial team and given a PIS to read in their own time. Patients will be offered the opportunity to ask questions, or advised to get in touch in order to address any questions that they may have on the contents of the PIS. If they decide to participate in the trial, they will undergo a screening assessment to confirm their eligibility for the trial as per inclusion/exclusion criteria described in section 9.1 and 9.2.

Screening assessments to establish eligibility will include:

- Age
- mJOA
- Planned Surgical Intervention
- DCM characteristics
  - Symptoms
  - Length of DCM symptoms
  - MRI image findings

- Number of cervical spine levels for treatment
- Neurological examination

*Estimated time: <30minutes.*

An anonymised record of the patients approached along with the numbers of, and reasons for, screen failures and refusal of consent will be kept at each site on a screening log and reported to the Trial Co-ordinating Centre on a monthly basis. This information will be used to identify any barriers to recruitment and allow improvement measures to be identified and implemented in a timely manner.

### 11.3.2 Participant Registration/Randomisation

Following screening, eligible subjects will be randomised to either laminectomy and or laminectomy and fusion. They will then be given a unique trial ID number.

## 11.4 Baseline Assessments

All participants will have a full medical history taken and a clinical examination. The following data points are to be recorded:

- Weight in Kg
- Gender
- DCM characteristics
- Smoking status (yes/no)
- Psychiatric comorbidities (yes/no)
- Impaired gait (yes/no)
- Medical History (Co-Morbidities)
- Medication History
- mJOA assessment
- SF36v2 (quality of life) score (physical component score and mental component score)
- EQ5D-5L
- Patient Health Questionnaire (PHQ9)
- Generalised Anxiety Disorder Questionnaire (GAD7)
- Neck Disability index (NDI)
- Brief Pain Inventory (BPI)
- Douleur Neuropathique 4 (DN4)
- Michigan Body Map (pain location)
- Cervical X-Rays (Deformity, Auto-fusion, Movement)
- Myelopathy.org symptom inventory
- (Updated) Charleston Comorbidity Index
- Healthcare Resource Use Questionnaire
- Optional assessments
  - MoveMed
  - Carer Quality of Life

Performed imaging, including the pre-existing MRI used for diagnosis and screening, will be centralised to further characterise the radiological features of a participants DCM, including cord compression and cervical spine alignment. The presence or absence of OPLL and on what basis (e.g., what form of imaging) was this determined, as this is relevant to the sensitivity of its detection, will however be recorded locally.

*Estimated time: 45minutes.*

## **11.5 Trial assessments**

### **11.5.1 Timing of assessments**

Post-operatively, participants are to be seen at their local hospital at 6-, 12- and 24-months post-surgery for assessments. Patients given additional consent, may also be followed up for an additional 60 ± 2 months, (5 years) subject to additional funding.

### **11.5.2 Intra-Operative Assessments**

- Operation title
- Cervical Levels treated
- American Society Anaesthesiology (ASA) grade
- Operation Duration
- Estimated Blood Loss
- Intra-operative complications
- Use of
  - Intra-operative Navigation
  - Intra-operative Neuromonitoring (neurophysiology)
- Nature of Inserted Metalwork, if applicable (number / brand)
- Use of synthetic products to support fusion, e.g. Actifuse, Baxter.

*Estimated time: 5minutes.*

### **11.5.3 Post-Operative Assessments on Discharge**

- Length of Stay and Ward Type
- Complications (including surgical site infection, wound breakdown, post-operative infection, post-operative medical complication e.g. PE)
- Other adverse events (E.g. requirement for blood transfusion)
- Change in Medication
- mJOA
- SF36v2
- EQ5D-5L
- NDI
- BPI
- DN4
- Michigan Body Map
- Cervical X-rays
- Optional
  - MoveMed
  - Carer Quality of Life

*Estimated time: 15minutes.*

### **11.5.4 Follow up Assessments at 6 months post-surgery (±21 days)**

- mJOA
- SF36v2 (Quality of life) Score
- EQ5D-5L

- Neck Disability Index (NDI)
- Brief Pain Inventory (BPI)
- Douleur Neuropathique 4(DN4)
- Michigan Body Map (Pain Location)
- Complications (including surgical site infection, wound breakdown, instrument failure)
- Adverse Events
- Cervical X-Rays (Deformity, Fusion, Movement)
- Myelopathy.org symptom inventory
- Change in Medication
- Healthcare Resource Use Questionnaire
- Optional
  - MoveMed
  - Carer Quality of Life

*Estimated time: 60minutes.*

#### 11.5.5 Follow up Assessments at 12 months post-surgery ( $\pm 21$ days)

- mJOA
- SF36v2 (Quality of life) Score
- EQ5D-5L
- Neck Disability Index (NDI)
- Brief Pain Inventory (BPI)
- Douleur Neuropathique 4(DN4)
- Michigan Body Map (Pain Location)
- Complications (including surgical site infection, wound breakdown, instrument failure)
- Adverse Events
- Cervical X-Rays (Deformity, Fusion, Movement)
- Myelopathy.org symptom inventory
- Change in Medication
- Healthcare Resource Use Questionnaire
- Optional
  - MoveMed
  - Carer Quality of Life

*Estimated time: 60minutes.*

- MRI Cervical Spine

A post-operative MRI Cervical Spine is performed by most, but not all surgeons, typically at 6-12 months. Therefore, as a secondary end, point this will be only be collected where performed.

*Estimated time: 30 minutes.*

#### 11.5.6 Follow up Assessments at 24 months - end of trial visit ( $\pm 21$ days)

- mJOA
- SF36v2 (Quality of life) Score

- EQ5D-5L
- Neck Disability Index (NDI)
- Brief Pain Inventory (BPI)
- Douleur Neuropathique 4(DN4)
- Michigan Body Map (Pain Location)
- Complications (including surgical site infection, wound breakdown, instrument failure)
- Adverse Events
- Cervical X-Rays (Deformity, Fusion, Movement)
- Myelopathy.org symptom inventory
- Change in Medication
- Healthcare Resource Usage Questionnaire
- Optional
  - MoveMed
  - Carer Quality of Life

*Estimated time: 60minutes.*

#### 11.5.7 Optional: Digital Endpoints, Continuous Monitoring

- MoveMed [Appendix 4]

MoveMed is a new remote monitoring tool for DCM, developed in response to the patient demand for an ambulatory assessment. DCM patients report a significant variation in symptoms, which cannot be captured by single time point: *“one day you can walk, one day you can’t”* and *“you look perfectly fine, you talk perfectly fine and all of a sudden y’ you’re on your back on the pavement and you can’t get up again”*

MoveMed uses a compatible smart-phone to collect quantitative and sensitive measurements of hand, arm and leg function using a combination of interactive on screen tests, and activity monitoring using the phone’s inbuilt sensors. Further information is detailed in Appendix 4.

MoveMed has received positive feedback, from testing in people with DCM and is being adopted into the Cambridge University Hospital, Spinal Cord Injury Pathway:

- *“This will enable you to get the whole picture of the disease, symptoms as a whole and not just a snapshot.”*
- *“As no two days are the same it would be good to have a record of how symptoms are and seeing if things are degenerating with something to show to a doctor.... And not be told it’s all in your head.”*

MoveMed will be an optional end-point in this trial, and eligible only to patients with a compatible smartphone. This is estimated to be approximately 50% of participants. A supplementary sheet will be provided to those interested, to complement their PIS.

#### 11.5.8 Optional: Carer Quality of Life

The impact of a chronic condition such as DCM is not restricted to the patient, as their disability can have an impact on the well-being and health of those, they subsequently live and/or depend on. In a pilot study of individuals reporting to be informal carers of

people with DCM, we identified a reduced quality of life using a tool called the Carer QOL. The Carer QOL has been designed, and extensively piloted across a range of cultures and languages. Measuring this impact has implications of health-economic outcomes and was a recommendation of the AO Spine RECODE-DCM Core Outcome Set.

Consequently, in this study, participants at baseline will be informed of option to measure CarerQOL and provided with a PIS to distribute to their informal carer(s). Contact details will be provided should the participant, or their informal carer(s) have follow up questions for the investigator team. Informal Carers consenting to participate will be sent a CarerQOL to complete at baseline, discharge from hospital, 6, 12 and 24 months after surgery.

#### 11.5.9 Table of Outcome Measures

Outcome	Timepoints	Assessor	Estimated Time to Complete (min)
Age	Baseline	Local team	1
Gender	Baseline	Local team	1
Medical History	Baseline	Local team	5
Medication History	Baseline, 6-, 12- and 24-months post-operatively	Local Team	5
Charleston Comorbidity Index	Baseline	Local Team	1
DCM characteristics	Baseline	Local Team (Additional Central Analysis)	5 (Baseline MRI will have already been performed)
Neurological examination	Baseline	Local team	5
Myelopathy.org symptom inventory	Baseline, 6-, 12- and 24-months post-operatively	Patient	20
Smoking status	Baseline	Local team	1
Psychiatric comorbidities	Baseline	Local team	1
Impaired gait	Baseline	Local team	2
Weight	Baseline	Local team	1
mJOA	Baseline, 6-, 12- and 24-months post-operatively	Central Team	5
SF36v2	Baseline, 6-, 12- and 24-months post-operatively	Patient (Administered Centrally)	10
EQ5D-5L	Baseline, 6-, 12- and 24-months post-operatively	Patient (Administered Centrally)	5
NDI	Baseline, 6-, 12- and 24-months post-operatively	Patient (Administered Centrally)	5
BPI	Baseline, 6-, 12- and 24-months post-operatively	Patient (Administered Centrally)	5
PHQ9	Baseline	Patient	5

		(Administered Centrally)	
GAD7	Baseline	Patient (Administered Centrally)	5
DN4	Baseline, 6-, 12- and 24-months post-operatively	Local team	2
Michigan Body Map	Baseline, 6-, 12- and 24-months post-operatively	Patient (Administered Centrally)	3
Complications	Baseline, intra-operative, immediately post-operatively, 6-, 12- and 24-months post-operatively	Local team	1
Cervical X-Rays	Baseline, post-operatively, 6-, 12- and 24-months post-operatively	Local Team (Analysis, Central)	5
Adverse event assessments	Baseline, intra-operative, immediately post-operatively, 6-, 12- and 24-months post-operatively	Local team	1
MRI Cervical Spine	12-months Post-Operatively	Local Team (Analysis, Central)	30
Healthcare Resource Usage Questionnaire	Baseline, 6-, 12- and 24-months post-operatively	Patient (Administered Centrally)	10

Preferentially, patient reported outcome measures conducted centrally will be captured using an electronic (web-based) form, directly by the participant. However, at the choice of the participant (and able to change in response to their requirements throughout the trial) this could alternatively be conducted using a paper, postal questionnaire or via telephone.

## 11.6 Schedule of Assessments

\* Optional

§ Performed by Significant Other, with their consent, and optional

Centralised

Assessment	Screening	Randomisation	Pre-operative baseline	Surgery	Post-operatively / Discharge	6 months post operatively (±21 days)	12 months post operatively (±21 days)	24 months post operatively (±21 days)
Informed consent	X							
Age	X							
Gender			X					
Medical History			X					
Medication History/Review			X		X	X	X	X
Charleston Comorbidity Index			X					
DCM characteristics	X		X					
Neurological examination	X							
Myelopathy.org symptom inventory [MOSI]			X			X	X	X
Smoking status			X					
Psychiatric comorbidities			X					
Impaired gait			X					
Randomisation		X						
Weight			X					
mJOA	X		X		X	X	X	X
SF36v2			X		X	X	X	X
EQ5D-5L			X		X	X	X	X
NDI			X		X	X	X	X
BPI			X		X	X	X	X
DN4*			X		X	X	X	X
Michigan Body Map*			X		X	X	X	X
Healthcare Resource Usage Questionnaire			X			X	X	X
PHQ9*			X					
GAD7*			X					
Complications				X	X	X	X	X
Cervical X-Rays			X		X*	X	X*	X
Operation title				X				
ASA grade				X				

Cervical levels treated				X				
Operation Duration				X				
Intra-Operative Blood Loss				X				
Adverse event assessments				X	X	X	X	X
Treatment details (e.g. procedure, intraoperative adverse events, use of navigation and neuromonitoring; type of metalwork and synthetic products used)				X				
Length of stay and Level of Care				X				
MRI Cervical Spine*							X	
MoveMed*			X	X	X	X	X	X
Carer Quality of Life§			X		X	X	X	X

## 11.7 Long-Term Follow-up Assessments

Subject to additional funding, and the provision of optional consent, it is proposed to conduct long-term follow-up for up to 5 years, using a combination of data linkage, to NHS Digital Hospital Episode Statistics, and telephone or electronic / postal follow up.

This will principally evaluate:

- (1) Healthcare Resource Usage (NHS Digital Linkage)
- (2) mJOA (Neurological Disability)
- (3) SF36 (Quality of Life)
- (4) BPI and NDI (Pain / Neck Disability)

The frequency and nature of this will be confirmed in due course, but as a minimum would make use of NHS Digital Hospital Episode Statistics.

## 11.8 End of Trial Participation

Trial participation will end 24 months post-surgery for each participant (unless consent has been given, and funding secured, for extended follow up). Following trial completion, patients will return to routine care as per their local centre protocols.

## 11.9 Trial restrictions

Beyond the inclusion and exclusion criteria, there are no specific restrictions to participation in this trial.

## 12 Assessment of Safety

### 12.1 Definitions

#### 12.1.1 Adverse event (AE)

Any untoward medical event in a participant of a clinical investigation which does not necessarily have a causal relationship to the intervention/treatment

An untoward medical event can include:

- any unintentional, unfavourable clinical sign or symptom
- any new illness or disease or the deterioration of existing condition
- any clinically relevant deterioration in any clinical tests

#### 12.1.2 Adverse reaction (AR)

All untoward and unintended responses to the clinical investigation treatment. All adverse events judged by either the reporting investigator or the sponsor as having a reasonable causal relationship to the treatment qualify as adverse reactions. The expression reasonable causal relationship means to convey in general that there is evidence or argument to suggest a causal relationship.

#### 12.1.3 Unexpected adverse reaction

An adverse reaction, the nature, or severity of which is not consistent with the known

safety information of the /intervention/treatment under investigation. When the outcome of the adverse reaction is not consistent with the applicable safety reference information (RSI) this adverse reaction should be considered as unexpected.

The term “severe” is often used to describe the intensity (severity) of a specific event. This is not the same as “serious,” which is based on participant /event outcome or action criteria.

#### 12.1.4 Serious adverse event or serious adverse reaction (SAE / SAR)

Any untoward medical occurrence that:

- results in death
- is life-threatening
- requires hospitalisation or prolongation of existing inpatients’ hospitalisation
- results in persistent or significant disability or incapacity
- is a congenital anomaly or birth defect.
- is an important medical event - Some medical events may jeopardise the participant or may require an intervention to prevent one of the above characteristics/ consequences. Such events (hereinafter referred to as ‘important medical events’) should also be considered as ‘serious’

Life-threatening in the definition of a serious adverse event or serious adverse reaction refers to an event in which the participant was at risk of death at the time of event; it does not refer to an event which hypothetically might have caused death if it were more severe.

## 12.2 Expected Adverse Reactions/Serious Adverse Reactions (AR /SARs)

The Health Research Authority (HRA) defines the terms **related** and **unexpected** as:

- **Related:** that is, it resulted from administration of any research procedures. All complications by definition are related to the trial procedures. (Untoward medical events which are unrelated to the trial procedures are not being collected in this trial.)
- **Unexpected:** that is, the type of event that in the opinion of the investigator is not considered expected. Examples of expected complications are provided in section 13.2; note this is not an exhaustive list.

Medical and scientific judgement must be exercised in deciding whether an event is serious (see section 12.4 for Responsibilities). These characteristics / consequences must be considered at the time of the event and do not refer to an event which hypothetically may have caused one of the above.

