#### 8.6.2 Secondary outcome measures

The following outcomes will be measured after surgery:

- Length of Hospital Stay
- Length of Operation

The following outcomes will be measured at 6-, 12- and 24-months post-surgery:

- SF36v2 (Quality of life) Score
- EQ5D-5L
- Neck Disability Index (NDI)
- Brief Pain Inventory (BPI)
- Douleur Neuropathique 4(DN4)
- Michigan Body Map (Pain Location)
- Surgical Complications (Defined by Tetreault et al 2019)
- Other Adverse Events, including mortality
- Cervical X-Rays (Alignment [C2–7 lordosis, C2–7 Sagittal Vertical Axis and T1 slope], Fusion, Movement)

The following outcomes will be measured at 12 months:

- MRI Cervical Spine (Decompression, Cord Signal Intensity)

These outcomes have been selected to align with the newly completed Core Outcome Set for DCM, in the absence of defined core measurement set at the time of trial set-up.

Domain	Outcome	Polyfix Tools
Neuromuscular	Neck Mobility	NDI

	Finger Strength	mJOA	
	Grip Strength	mJOA	
	Finger/Hand Dexterity	mJOA	
	Arm Weakness	mJOA	
	Leg Weakness	mJOA	
	Balance	mJOA	
	Sensory Dysfunction	mJOA	
	Bladder Dysfunction	mJOA	
	Faecal Incontinence	SF36v2	
Life Impact	Falls	EQ5D-5L	
	Mobility	mJOA	
		EQ5D-5L	
		SF36v2	
	Dependence	EQ5D-5L	
	Fatigue	SF36v2	
EQ5D-5L			
Pain	Mental Health	SF36v2	
		SF36v2	
		Location	Michigan Body Map
		Intensity	BPI
		Perception	BPI / DN4
Radiology	Pain Control	BPI	
	Cord Compression	Post-Operative MRI	
		Cord Signal Change	Post-Operative MRI
		Alignment	Post-Operative Cervical X-Rays
	Adjacent Segment Disease	Post-Operative MRI	
Economic Impact	Employment Status	Healthcare Resource Use Questionnaire	
	Cost of Care	Length of Stay	
Length of Operation		Healthcare Resource Use Questionnaire	
			Healthcare Resource Use Questionnaire
Adverse Events	Death	Other Adverse Effects	
	Surgical complications	Surgical Complications 	

With the exception of radiological outcomes (X-Ray and MRI Imaging), and an assessment of adverse events, including surgical complications, participants will be followed up using electronic or postal questionnaires ± telephone consultation. If the time point after an assessment exceeds 8 weeks, and there is no response, then the patient will be deemed as lost to that follow up.

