## 12.4 Evaluation of adverse events

The Sponsor expects that adverse events are recorded from the point of Informed Consent regardless of whether a participant has yet received a research procedure. Individual adverse events should be evaluated by the investigator. This includes the evaluation of its seriousness, and any relationship between the investigational medicinal product(s) and/or concomitant therapy and the adverse event (causality).

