### **12.5 Reporting serious adverse events**

Each Principal Investigator needs to record all adverse events and report serious adverse events to the Chief Investigator using the trial specific SAE form within 24 hours of their awareness of the event.

The Chief Investigator is responsible for ensuring the assessment of all SAEs for expectedness and relatedness is completed and the onward notification of all SAEs to the Sponsor immediately but not more than 24 hours of first notification. The sponsor has to keep detailed records of all SAEs reported to them by the trial team.

The Chief Investigator is also responsible for prompt reporting of all serious adverse event findings to the relevant authorities of each concerned Member State if they could:

- adversely affect the health of participants
- impact on the conduct of the trial
- alter the risk to benefit ratio of the trial

The completed SAE form can be emailed. Details of where to report the SAE's can be found on the POLYFIX DCM SAE form and the front cover of the protocol.

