### **15.5 Procedure to account for missing or spurious data**

The data will be analysed in two populations, a safety population that includes all patients who have consented to the trial, and a full analysis population that include all patients who are randomised. Groups will be allocated using the ITT principle that looks at which arm they were randomised to, disregarding subsequent deviations from protocol.

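### Section 12.2 excludes unrelated adverse events that sections 12.4 and 12.5 require to be recorded, and the 15.5 safety population includes people who have no arm

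*Protocol*

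**What the plan says.** On what is collected, the protocol gives these statements:

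- Section 12.2, inside its definition of a related event: "Untoward medical events which are unrelated to the trial procedures are not being collected in this trial". The sentence before it makes every complication related by definition.
- Section 12.1.1 defines an adverse event without requiring any causal link to treatment.
- Section 12.4: "The Sponsor expects that adverse events are recorded from the point of Informed Consent regardless of whether a participant has yet received a research procedure".
- Section 12.4.2 has five causality grades. Two of them, *Unlikely* and *Unrelated*, are classed as adverse events that are not related to the intervention.
- Section 12.5: "Each Principal Investigator needs to record all adverse events and report serious adverse events". The Chief Investigator must also ensure that every serious adverse event is assessed for relatedness.
- Section 8.6.2 lists as a secondary outcome: "Other Adverse Events, including mortality".

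On when recording starts, section 12.4 says consent, the outcome table in 11.5.9 lists baseline as the first time point for adverse event assessment, and the schedule in 11.6 first marks it at surgery.

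On the analysis set, section 15.5 defines "a safety population that includes all patients who have consented to the trial", and a full analysis population of all randomised patients. It then gives one grouping rule for both: "Groups will be allocated using the ITT principle that looks at which arm they were randomised to".

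**The concern.** A site that follows 12.2 and a site that follows 12.4 and 12.5 would send in different data for the same patient. Under 12.2, relatedness becomes a condition of entry. The outcome table in 11.5.9 gives adverse event assessment to the local team, and section 9.4 says the clinical teams cannot be blinded. An unblinded local judgement could therefore decide whether an event reaches the database at all. Several events on the expected list in 12.3, such as respiratory infection, myocardial infarction and stroke, are hard to attribute with confidence.

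The synopsis plans to compare adverse events between the arms. Section 15.4 sets no stopping criteria beyond the pilot, so the data monitoring committee depends on the accumulating safety data. Events that were never entered may be hard to recover later.

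The population wording raises a separate problem: a safety table by randomised arm cannot hold someone who was never given an arm.

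**Working it through.** The point disputes no figure in the protocol. The nearest one, the sample size, was checked and stands. For a 1-point difference, SD 2.89, two-sided 5% and 90% power, a two-sample t-test needs 177 per arm. Then 177 / 0.9 = 196.7, rounded up to 197, and 2 × 197 = 394, as section 15.3 states.

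**Step 1. Apply each rule to the same event.**

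| Event | Section 12.2 | Sections 12.4, 12.4.2 and 12.5 |
|---|---|---|
| Surgical complication | Collected (related by definition) | Collected |
| Event after consent, before any procedure | Not collected, since it can hardly result from a procedure not yet done | Recorded |
| Follow-up event graded *Unlikely* or *Unrelated* | Not collected | Recorded and graded |
| Death from an unrelated cause | Not collected on a literal reading | Serious by 12.1.4 whatever the cause; reported under 12.5; part of an 8.6.2 outcome |

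The rules agree on the first row only. Under 12.2 the two lowest causality grades would have nothing to grade.

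**Step 2. Start point.** Consent (12.4), baseline (11.5.9) and surgery (11.6) are three different starts. Section 8.4 gives an average wait for surgery of 79 days, so the choice covers a period of real length.

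**Step 3. Size of the numerator gap.** The protocol gives no share of unrelated events, so this is an assumed range. If a share *u* of all adverse events is unrelated, the ratio of the count under 12.4 and 12.5 to the count under 12.2 is 1 / (1 − *u*):

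- *u* = 20%: 1 / 0.80 = 1.25
- *u* = 40%: 1 / 0.60 = 1.67
- *u* = 60%: 1 / 0.40 = 2.5

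This concerns the total adverse event count, not the complication count.

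**Step 4. Who has no arm.** Consent precedes any trial-specific activity (11.2), eligibility is confirmed by screening after that (11.3.1), and only eligible people are randomised (11.3.2). With 394 randomised and an assumed share *f* of consented people never randomised, the number without an arm is 394 / (1 − *f*) − 394:

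- *f* = 2%: 402 − 394 = 8
- *f* = 5%: 415 − 394 = 21
- *f* = 10%: 438 − 394 = 44

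These people belong to the safety population of 15.5 but cannot be grouped by its rule.

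**The case against.** Four objections deserve an answer.

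*The filter does not reach the events that matter most for fusion.* This stands. Complications, including instrument failure, are related by definition and are scheduled items during and after surgery. A reader might infer that the whole safety comparison lacks a defined numerator; the text supports that only for other adverse events, serious adverse events and deaths.

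*Deaths are not lost.* This largely stands. A reader might infer that deaths judged unrelated disappear from the trial. But mortality is a named outcome, any event resulting in death is serious whatever its cause, and serious events go to the Chief Investigator within 24 hours, so the local judgement is not the only one. The sentence in 12.2 also sits inside a definition. A site could still apply it literally, so incomplete capture of deaths is a risk and not a certain result.

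*Grouping by randomised arm is legitimate.* This stands. It is a valid safety comparison of two surgical strategies in a pragmatic trial. A reader might infer that the denominators of both arms are wrong, or that the risk difference is diluted by a known amount. The protocol gives no crossover or non-operation rate, so no such amount follows from it. People without an arm cannot dilute either arm's rate. Operation title and inserted metalwork are recorded (11.5.2), so a table by operation performed remains possible.

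*The analysis plan can settle this.* That holds for the choice of tables, but not for the collection rule. An analysis plan cannot restore events that sites were told not to enter.

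**Conclusion.** The collection rules contradict each other in the protocol's current text. The conflict is limited to other adverse events, serious adverse events and deaths, and to when recording begins. Its size cannot be taken from the protocol: the factor of 1.25 to 2.5 in total adverse events rests on an assumed unrelated share of 20% to 60%. Whether sites in fact follow different rules is unknown, so different ascertainment by site or by arm is a possibility and is not shown.

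The population wording in 15.5 is a second, smaller fault: the grouping rule cannot be carried out for every member of the safety set. The assumed 8 to 44 people are only an illustration, and they do not change any rate within an arm.

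Section 15.1 makes the adverse event and complication analyses descriptive, so no test, power or sample size is affected. This should be fixed, preferably while data are still being collected, but it does not threaten the primary comparison.

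**What to change.** **Collection.** Delete the parenthetical sentence in 12.2, or otherwise reconcile 11.5.9, 11.6, 12.2, 12.4, 12.4.2 and 12.5 into one rule with one start point. Record relatedness as an attribute of an event and not as a condition for entering it. State explicitly that deaths from any cause are captured.

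**Analysis set.** In 15.5:

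- restrict the comparative safety set to randomised participants and keep the table by randomised arm;
- add beside it a table of procedure- and implant-related events among operated participants, by operation performed;
- list events in consented but unrandomised people separately.

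**Cost.** A protocol wording amendment and a note to sites. If all events are to be entered, sites that have followed 12.2 will enter more than before, although 12.5 already asks for this. The table by operation performed is not protected by randomisation, because the reasons for changing operation may be related to risk. It should therefore accompany the table by randomised arm and not replace it.
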